6.2.4 Conventions for Missing and Partial Dates

All rules explained below for partial / missing dates will be followed unless contradicted by any other data recorded on the electronic Case Report Form (eCRF).

All dates presented in the individual subject listings will be as recorded on the eCRF (i.e., not completed as per the below rules).

6.2.5 Missing / Partial Start / Stop Date of Adverse Events (AE) and Concomitant Medications

Missing and partial start and stop dates will be imputed for analysis purposes as follows.

Partial or missing stop date will be imputed as follows:

If the stop date is completely missing and the event has resolved, or the subject has stopped taking the concomitant medication, the stop date will be imputed as the date of the subject’s last clinic visit in the study.

- If only the year is known, the stop date will be imputed as “31-Dec” of that year or as the date of the subject’s last clinic visit in the study if in the same year.
- If the month and year are known, the stop date will be imputed as the last day of that month unless the stop date corresponds to the same month as the subject’s last clinic visit in which case the date of subject’s last clinic visit in the study will be used instead.

Missing start date will be imputed as follows:

- If the stop date occurs on or after the start of study drug or the event / concomitant medication is ongoing, the start date will be imputed as the date of the first dose of study drug.

QMD Ref: Worldwide-TMP-ST-005-7.0 Effective: 12Aug2019	Governing QMD: Worldwide-SOP-ST-001
Confidentiality Statement	

This document is the property of Worldwide Clinical Trials Inc. and may not be duplicated, copied, altered or removed from company without prior approval from Worldwide Quality Assurance or in compliance with Worldwide Standard Operating Procedures.

Worldwide Clinical Trials Controlled Quality Management Document			
 WORLDWIDE CLINICAL TRIALS	Sponsor:	Helixmith Co., Ltd.	
Protocol Number:			VMALS-002-2b
STATISTICAL ANALYSIS PLAN. PHASE 2-3-4			

- If the stop date occurs before the start of study drug, the start date of the event / concomitant medication will be imputed as the subject's screening date or the stop date of the event / concomitant medication whichever is earlier.

Partial start date (year present, but month and day missing)

- If the stop date occurs on or after the start of study drug or the event / concomitant medication is ongoing, and the year is the same as the year of first dosing, the start date will be imputed as "01-Jan" of the same year or the date of the first dose of study drug whichever is the latest. If the year is different from the year of first dosing "01-Jan" will be used.
- If the stop date occurs before the start of study drug, the start date of the event / concomitant medication will be imputed as the "01-Jan" of the same year.

Partial start date (month and year present, but day missing)

- If the stop date occurs on or after the start of study drug or the event / concomitant medication is ongoing, the start date will be imputed as the first day of the same month and year unless this partial start date is in the same month as the first dose of study drug in which case, the date of first dose of study drug will be used.
- If the stop date occurs before the start of study drug, the start date will be imputed as the first day of the month and year of the partial stop date.

If the start time is missing it will be imputed only in the case where the start date of the concomitant medication / event corresponds to the date of the first dose of study drug. The time will be imputed as the same time as the first dose of study drug. In all other cases the time will not be imputed.

6.2.6 Missing Last Dates of Study Drug Dosing

Not applicable in this SAP.

6.2.7 Missing Diagnosis Dates

If the month and year are present but the day is missing, the diagnosis date will be set to first day of the relevant month. If only the year is recorded the diagnosis date will be set as "01-Jan" for that year.

6.2.8 Exposure to Study Drug

Not applicable in this SAP.

QMD Ref: Worldwide-TMP-ST-005-7.0 Effective: 12Aug2019	Governing QMD: Worldwide-SOP-ST-001
Confidentiality Statement	

This document is the property of Worldwide Clinical Trials Inc. and may not be duplicated, copied, altered or removed from company without prior approval from Worldwide Quality Assurance or in compliance with Worldwide Standard Operating Procedures.

Worldwide Clinical Trials Controlled Quality Management Document			
 WORLDWIDE CLINICAL TRIALS	Sponsor:	Helixmith Co., Ltd.	
Protocol Number:			VMALS-002-2b
STATISTICAL ANALYSIS PLAN. PHASE 2-3-4			

6.2.9 Revised Amyotrophic Lateral Sclerosis Functional Rating Scale (ALSFRS-R)

Subscore for Fine and Gross Motor Functions will be calculated as sum of scores for items 4 to 9; subscore for Bulbar Function will be calculated as sum of scores for items 1 to 3. Total score will be calculated as sum of scores for items 1 to 9.

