1.1. Synopsis

Protocol Title: A 6-Month Extension Study Following Protocol VMALS-002-2 (A Phase 2a, Double-Blind, Randomized, Placebo-Controlled, Multicenter Study to Assess the Safety of Engensis in Participants with Amyotrophic Lateral Sclerosis)

Short Title: A 6-Month Extension Study to Assess the Safety of Engensis in Amyotrophic Lateral Sclerosis

Rationale:

The purpose of this study is to evaluate the long-term safety of intramuscular (IM) administration of Engensis in Participants with Amyotrophic Lateral Sclerosis (ALS) who were previously randomized, received treatment, and completed the Day 180 Visit of Study VMALS-002-2. Safety will be assessed by incidences of treatment-emergent adverse events (TEAEs), treatment-emergent serious adverse events (TESAEs), adverse events of special interest (AESIs), and the clinically significant laboratory values. See the table below for additional, exploratory endpoints.

Engensis contains the active pharmaceutical ingredient VM202, a novel genomic complementary deoxyribonucleic acid (cDNA) hybrid human hepatocyte growth factor (HGF) coding sequence (HGF-X7) expressing two isoforms of HGF, HGF₇₂₈ and HGF₇₂₃, being developed by Helixmith for treatment of ALS.

Data from Helixmith's first clinical trial in ALS, the Phase 1/2 study (VMALS-001) that included 18 Participants who were followed for 9 months, suggested that targeted delivery of HGF to motor neurons via intramuscular (IM) injections of Engensis was safe and well-tolerated. Safety assessments during the study included reports of 79 adverse events (AEs) in 17 Participants (94.4%), including 26 mild injection site reactions (Grade 1). Five SAEs were reported in 3 Participants. Only an injection site reaction was considered related to study treatment. Following injections until Day 90, a plateau or a relative slowing in the decline of the Revised Amyotrophic Lateral Sclerosis Function Rating (ALSFRS-R) scores and muscle strength was noted, suggesting a slowing of disease progression. After 90 days, the plateau was no longer observed in the ALSFRS-R, with the notable exception of a trend toward better preservation of bulbar and breathing functions as measured by the ALSFRS-R.

Data for Participants at study visits in Study VMALS-002-2 will be used as reference points for changes in safety assessments during the extension study VMALS-002-2b.

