8.2. Other Assessments and Procedures

8.2.1. Revised Amyotrophic Lateral Sclerosis Functional Rating

The ALSFRS-R is a validated rating scale for measuring the global function of patients with ALS. It provides a health professional-generated estimate of the patient's degree of functional impairment, which can be evaluated serially to objectively assess any response to treatment or progression of disease. The ALSFRS-R includes twelve questions that ask the Investigator to rate his/her impression of the patient's level of functional impairment in performing one of twelve common tasks, e.g., climbing stairs. Each task is rated on a five-point scale from 0 (can't do) to 4 (normal ability). Individual item scores are summed to produce a reported score between 0=worst and 48=best. The ALSFRS-R will be conducted on Days 240, 300, and 365/ET. Details about the scale can be found in Section 10.4, Appendix 4.

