6.15 Exploratory Analyses

6.15.1 Revised Amyotrophic Lateral Sclerosis Functional Rating Scale (ALSFRS-R)

ALSFRS-R will be measured at Day 240, Day 300 and Day 365. Total score and subscores for Fine and Gross Motor Functions (sum of scores for items 4 to 9) and for Bulbar Function (sum of scores for items 1 to 3) their changes from baseline will be presented with descriptive statistics by visits and treatment group (Table 14.6.1, Listing 16.2.9.1).

Slope of the total score will be provided using graphical presentation of values by visit for both treatment group. The figures will be presented using time points from both VMALS-002-2 and VMALS-002-2b studies.

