9 CHANGES TO PLANNED PROTOCOL ANALYSIS

There are no changes to the planned protocol analysis.

QMD Ref: Worldwide-TMP-ST-005-7.0 Effective: 12Aug2019	Governing QMD: Worldwide-SOP-ST-001
Confidentiality Statement	

This document is the property of Worldwide Clinical Trials Inc. and may not be duplicated, copied, altered or removed from company without prior approval from Worldwide Quality Assurance or in compliance with Worldwide Standard Operating Procedures.

Worldwide Clinical Trials Controlled Quality Management Document			
 WORLDWIDE CLINICAL TRIALS	Sponsor:	Helixmith Co., Ltd.	
	Protocol Number:	VMALS-002-2b	
STATISTICAL ANALYSIS PLAN. PHASE 2-3-4			

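### The SAP's ALSFRS-R total sums items 1 to 9 and leaves out the three breathing items, so it is not the protocol's 0–48 score

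*SAP*

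**What the plan says.** Protocol 8.2.1 describes the instrument: "The ALSFRS-R includes twelve questions that ask the Investigator to rate his/her impression of the patient's level of functional impairment". Each item runs from 0 to 4, and "Individual item scores are summed to produce a reported score between 0=worst and 48=best". Appendix 4 of the protocol names items 10, 11 and 12 as dyspnea, orthopnea and respiratory insufficiency.

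The endpoint lists (Protocol 3, SAP 3.2) include change from Baseline to Day 365 in the total ALSFRS-R score and the slope of that total over time. They restrict items only for the subscores: items 4 to 9 for motor function and items 1 to 3 for bulbar function.

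SAP 6.2.9 repeats the two subscores and then says: "Total score will be calculated as sum of scores for items 1 to 9". SAP 6.15.1 tabulates the total without redefining it and adds: "Slope of the total score will be provided using graphical presentation of values by visit for both treatment group". SAP 9 states: "There are no changes to the planned protocol analysis".

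**The concern.** The protocol and the SAP give the same name, total ALSFRS-R, to two different scores. A programmer working from SAP 6.2.9 would produce a nine-item score that contains no breathing item. A reader of the study report would reasonably take it for the 0–48 score the protocol describes.

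The omission could mislead in either direction, by hiding respiratory worsening or by hiding respiratory preservation. The domain matters to this sponsor: the protocol synopsis reports from VMALS-001 a "trend toward better preservation of bulbar and breathing functions as measured by the ALSFRS-R". The SAP total cannot reflect the breathing part of such a trend, and no respiratory subscore is planned.

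Nothing suggests a deliberate choice. Neither document gives a reason for a nine-item score. The omitted items belong to the same scheduled assessment, and SAP 6.2.3 uses the answer to item 12 to define the tracheostomy event. The SAP thus relies on an item that it leaves out of the total.

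**Working it through.** **Inputs**

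- Number of items: 12 (Protocol 8.2.1).
- Points per item: 0 to 4 (Protocol 8.2.1).
- Protocol range of the total: 0 to 48 (Protocol 8.2.1).
- Items in the SAP total: 1 to 9 (SAP 6.2.9).
- Items in the subscores: bulbar 1 to 3, motor 4 to 9 (SAP 6.2.9).

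**Step 1: reproduce the protocol's figure.** Maximum = items × 4 = 12 × 4 = 48. This matches the protocol.

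**Step 2: apply the SAP rule.** Maximum = 9 × 4 = 36, so the range is 0–36.

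**Step 3: size of the omission.** Items 10 to 12 carry 3 × 4 = 12 points. 48 − 36 = 12, and 12 / 48 = 25% of the scale.

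**Step 4: what the SAP total consists of.** Bulbar maximum = 3 × 4 = 12, motor maximum = 6 × 4 = 24, and 12 + 24 = 36. For each participant the SAP total is exactly the sum of the two subscores already tabulated.

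**Step 5: effect on a participant's change score.** Suppose only items 10 to 12 change.

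| Change on items 10–12 | Protocol total | SAP total |
|---|---|---|
| Each item falls by 1 point | −3 | 0 |
| Each item falls from 4 to 0 | −12 | 0 |

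The second row is the ceiling. The documents give no expected change on these items, so the typical loss cannot be stated.

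**Step 6: look for a rescue elsewhere.** SAP 3.2 calls the measure the total and sets no item limit. SAP 6.15.1 uses the total without redefining it. SAP 9 lists no change. SAP 6.2.9 is therefore the operative derivation.

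**The case against.** The contradiction itself is hard to dispute. The case on the other side concerns how much it matters.

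- **The endpoints are exploratory.** ALSFRS-R is summarised descriptively, the slope is a graph with no model or test, at most 18 participants can enrol, and the primary endpoints are safety incidences. This stands. No test, error rate or sample size depends on the score.
- **Breathing is assessed elsewhere.** SVC has its own analysis (SAP 6.15.5), time to tracheostomy is built from item 12, and pulmonary events are adverse events of special interest. This also stands: the total is blind to breathing decline, but the plan as a whole is not. ALSFRS-R data will be listed, so the correct total may be recoverable, although SAP 6.15.1 does not say that the listing is item by item.
- **The VMALS-001 argument is limited.** The signal reported there was specific to certain domains. A twelve-item total would include breathing but not isolate it; only a respiratory subscore would do that. Nor do the documents say how the VMALS-001 total was scored, so non-comparability with that study is an inference. Non-comparability with any 0–48 result is arithmetic.
- **The nine-item total is not wholly redundant.** It is the sum of the subscores for each participant, but its SD, median, range and confidence limits cannot be recovered from the subscore summaries. This is correct.
- **It might be intended.** The endpoint list says only that the score is the total; the 0–48 range sits in the assessment section. But a deliberate nine-item score would need to be declared in SAP 9, and it is not.

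These points narrow the consequences. None makes the nine-item sum the score that the protocol describes.

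**Conclusion.** The concern holds. SAP 6.2.9 defines a 0–36 score, the protocol defines 0–48, and the 12 points lost (25%) are all the breathing items. Programmed as written, the SAP would give wrong values for the total in Table 14.6.1 and in the slope figure, which are the outputs for two listed endpoints.

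The conclusion rests on reading the endpoint's total as the score in Protocol 8.2.1, which is the only total either document describes besides the SAP's own. The 12 points are a maximum per participant; the expected effect is unknown. The consequence is confined to exploratory, descriptive results. It should nevertheless be corrected before the tables are programmed, because it is an error in a derivation and not a matter of preference.

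**What to change.** In SAP 6.2.9, define the total score as the sum of items 1 to 12, range 0–48. Use it for Table 14.6.1, Listing 16.2.9.1 where the total appears, and the slope figure, at every time point from both VMALS-002-2 and VMALS-002-2b so that Baseline and follow-up are on the same scale.

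Optionally, add a respiratory subscore (items 10 to 12, range 0–12) beside the two existing ones. That is the summary that would let the breathing domain be seen separately.

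If a nine-item score was intended, give it another name, justify it in SAP 9, and still report the 0–48 total.

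The required change costs one line of SAP text and one line of derivation code. It needs no new data, and I see no drawback.

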6.2.10 Amyotrophic Lateral Sclerosis Assessment Questionnaire (ALSAQ-40)

The questionnaire consists of 40 questions (Q1-Q40), which are converted to 5 subscales using the following rules (according to the ALSAQ User Manual):

PHYSICAL MOBILITY = $((Q1 + Q2 + Q3 + Q4 + Q5 + Q6 + Q7 + Q8 + Q9 + Q10)/40) \times 100$.

ACTIVITIES OF DAILY LIVING/INDEPENDENCE = $((Q11 + Q12 + Q13 + Q14 + Q15 + Q16 + Q17 + Q18 + Q19 + Q20)/40) \times 100$.

EATING AND DRINKING = $((Q21+Q22+Q23)/12) \times 100$.

COMMUNICATION = $((Q24 + Q25 + Q26 + Q27 + Q28 + Q29 + Q30) / 28) \times 100$.

EMOTIONAL FUNCTIONING = $((Q31 + Q32 + Q33 + Q34 + Q35 + Q36 + Q37 + Q38 + Q39 + Q40)/40) \times 100$.

If a subscale of the questionnaire has less than 50% of the questions correctly answered, it should be considered as missing.

The following approaches will be used in case of missing or incorrectly answered questions:

- Worst values will be imputed
- Average value of correctly filled questions of the subscale

Results of both approaches will be presented in separate tables. Subscale values will be presented with 1 decimal place. Number of decimal places for descriptive statistics will be presented using rules in Section 6.3.1.

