6.15.3 Amyotrophic Lateral Sclerosis Assessment Questionnaire, 40 questions (ALSAQ-40)

ALSAQ-40 will be measured at Day 240 and Day 365. Values of each question, subscales (Physical Mobility, Activities of Daily Living/Independence, Eating and Drinking, Communication and Emotional Functioning) with imputed values as described in section 6.2.10 and their changes from baseline will be presented with descriptive statistics for each visit by treatment group (Tables 14.3.6.4.1-14.3.6.4, Listing 16.2.9.4).

6.15.4 Clinical Global Impression of Change (CGIC) and Patient Global Impression of Change (PGIC)

QMD Ref: Worldwide-TMP-ST-005-7.0 Effective: 12Aug2019	Governing QMD: Worldwide-SOP-ST-001
Confidentiality Statement	

This document is the property of Worldwide Clinical Trials Inc. and may not be duplicated, copied, altered or removed from company without prior approval from Worldwide Quality Assurance or in compliance with Worldwide Standard Operating Procedures.

Worldwide Clinical Trials Controlled Quality Management Document			
 WORLDWIDE CLINICAL TRIALS	Sponsor:	Helixmith Co., Ltd.	
	Protocol Number:	VMALS-002-2b	
STATISTICAL ANALYSIS PLAN. PHASE 2-3-4			

CGIC and PGIC will be measured at Day 240 and Day 365. Global improvement, Efficacy index, Impression of change and Degree of Change will be presented with descriptive statistics for each visit by treatment group (Tables 14.6.5 and 14.6.6, Listings 16.2.9.5 and 16.2.9.6).

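### As written, the ALSAQ-40 worst-value imputation also covers baseline, where it biases within-arm change towards improvement

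*SAP*

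**What the plan says.** SAP 6.2.10 holds the only ALSAQ-40 scoring rules in the documents: five subscale formulas and two ways of filling items. The trigger is worded "The following approaches will be used in case of missing or incorrectly answered questions". The two approaches are "Worst values will be imputed" and "Average value of correctly filled questions of the subscale". On reporting, the SAP says "Results of both approaches will be presented in separate tables". There is one floor: "If a subscale of the questionnaire has less than 50% of the questions correctly answered, it should be considered as missing". The section names no visit, so baseline is neither included nor excluded explicitly. Neither approach is called the main one.

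SAP 6.15.3 then presents the subscales "with imputed values as described in section 6.2.10 and their changes from baseline", by visit and treatment group. SAP 6.2.2 takes baseline as the latest available pre-injection value from the parent study, VMALS-002-2. SAP 6.3 adds 95% confidence limits for the mean change in each arm. The endpoint in SAP 3.2 is exploratory: ALSAQ-40 change from Day 0 to Day 365, Engensis against placebo.

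**The concern.** Worst-value imputation is normally chosen because it is conservative: an unanswered item counts against the participant. That holds only after baseline. The response options run from never to always or unable (Protocol 8.2.3.1 and Appendix 5), so a higher score is worse. Change is Day 365 minus baseline. A worst value placed in the baseline form raises the number being subtracted and moves the change towards improvement. ALS is progressive, so baseline answers will tend to lie further from the worst value than later ones, and the rule is least defensible at that visit.

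If the rule is programmed as it reads, one of the two sets of ALSAQ-40 tables carries a one-directional baseline error for every participant with an incomplete baseline form. The two sets can then disagree for a reason unrelated to treatment, and the SAP does not say which one leads.

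**Working it through.** The documents give no effect size, variance or missing-item rate for this endpoint, so there is no planned figure to reproduce. The check scores the subscales directly.

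**Inputs**
- Divisors 40, 40, 12, 28 and 40 for subscales of 10, 10, 3, 7 and 10 items (SAP 6.2.10). These imply items coded 0 to 4 with 4 worst. The coding is inferred, not stated.
- A subscale is kept if at least half of its items are answered (SAP 6.2.10). At most 5 of 10, 3 of 7 or 1 of 3 items can therefore be imputed.
- At most 18 participants (SAP 4). Arm sizes are not given; 6, 9 and 12 are assumed to show a range.

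**Baseline error.** For a subscale of k items, setting one blank item with true value t to 4 raises the baseline score by (4 − t)/(4k) × 100. The same amount is subtracted from the change. The error is never negative. It is largest at t = 0 and zero at t = 4.

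| Subscale | Items | Largest error, one blank (t = 0) | Largest error, most blanks allowed | Stable participant, all items 1, one baseline blank |
|---|---|---|---|---|
| Each 10-item subscale | 10 | 4/40 = 10.0 | 20/40 = 50.0 | −3/40 = −7.5 |
| Communication | 7 | 4/28 = 14.3 | 12/28 = 42.9 | −3/28 = −10.7 |
| Eating and Drinking | 3 | 4/12 = 33.3 | 4/12 = 33.3 | −3/12 = −25.0 |

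The fractions are multiplied by 100. The true change in the last column is 0.

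**Participant who truly worsens**, every item going from 1 to 2 (true change +25.0), with the blanks at baseline only:
- 10-item subscale, one blank: 20/40 − 13/40 = 50.0 − 32.5 = +17.5. Decline is understated, but no improvement appears.
- Eating and Drinking, one blank: 6/12 − 6/12 = 0.0. The decline disappears.
- 10-item subscale, five blanks: 20/40 − 25/40 = 50.0 − 62.5 = −12.5. The sign reverses.

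**When there is no net error.** If the true baseline item was already 4, the error is 0. If the same item is blank at both visits, both are set to 4 and the item contributes no change, which is right for a stable item.

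**Effect on an arm mean** of one participant with one blank baseline item (error divided by arm size):

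| Blank item | Arm of 6 | Arm of 9 | Arm of 12 |
|---|---|---|---|
| Eating and Drinking, true 0 (33.3) | 5.6 | 3.7 | 2.8 |
| Eating and Drinking, true 1 (25.0) | 4.2 | 2.8 | 2.1 |
| 10-item subscale, true 1 (7.5) | 1.25 | 0.83 | 0.625 |

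**The other planned approach.** In the stable example above, filling with the average of answered items gives a change of 0.0. It is not free of error. With ten baseline items of one 0, eight 1s and one 2 (true score 25.0), blanking the 0 gives 27.8 and blanking the 2 gives 22.2. Those errors can fall either way; the worst-value error at baseline cannot.

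**The case against.** The strongest reply is that the SAP never says the rule is used at baseline. Baseline forms come from the parent study, whose scoring rules are not in these documents. SAP 6.2.2 could also fill a blank Day 0 item from an earlier pre-injection answer, since it does not say whether it works per item or per subscale. This stands in part: baseline use is inferred from an unrestricted rule. But change from baseline needs a scored baseline, and SAP 6.2.10 is the only scoring rule available. Under that rule a half-complete subscale already counts as non-missing, so a look-back per subscale would not be triggered. A look-back per item helps only if an earlier answer exists.

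Second, the average-item tables are already planned and avoid the one-directional error, so a reader would see the contrast. That is true, and it limits the harm. It does not settle which table to believe.

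Third, a reader might infer that the rule favours Engensis. The documents do not support that. Baseline items are answered before the first injection in a randomised, double-blind parent study (Protocol 4.2), so treatment cannot cause a blank baseline item. What remains is bias in within-arm change, plus chance imbalance in small arms.

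Finally, the questionnaire is captured electronically (Protocol 8.2.3.1), so blanks may be rare. The largest figures also need true answers of 0 and, for 50.0 and 42.9, several blanks in one participant. Both points stand.

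**Conclusion.** The point holds as a defect in a stated rule: followed literally, SAP 6.2.10 is anti-conservative at baseline. The size is at most 10.0, 14.3 or 33.3 points per blank item in one participant, and about 2 to 6 points on an arm mean for one blank Eating and Drinking item. This rests on the inferred 0 to 4 coding, on reading the unrestricted rule as including baseline, and on assumed arm sizes of 6 to 12 with a true item of 0 or 1.

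It would be tempting to say that a blank baseline item always yields a false improvement at Day 365. It does not: the error may be zero, may cancel, or may only understate a real decline. The actual effect cannot be sized, because no blank-item rate is given. No primary or safety conclusion depends on this exploratory, descriptive endpoint. The point should be corrected before database lock, but it does not threaten the study's main purpose.

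**What to change.** In SAP 6.2.10:
- Name the average-of-answered-items version, applied at every visit including baseline, as the main ALSAQ-40 analysis.
- Keep the worst-value version as a sensitivity analysis, with the worst value used at post-baseline visits only and baseline scored by the average of answered items.
- State that this sensitivity analysis is deliberately conservative and will show worsening when the same item is blank at both visits. For a stable participant with all items at 1, one such item gives +7.5 points on a 10-item subscale (13/40 − 10/40) and +25.0 on Eating and Drinking (6/12 − 3/12).

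The cost is a few sentences in the SAP and one programming condition on visit. The two sets of tables stay as planned, and no new data are needed. The downside is the loss of cancellation for items blank at both visits. That is acceptable in an analysis labelled as the conservative bound, and it does not affect the main one.
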